6.3.9 Concomitant Medication

All concomitant medications/therapies for the 5-7-years follow-up visit will be summarised as number of patients being treated with each type of medication/therapy classified according to ATC level 3 group text and World Health Organization (WHO) Drug Dictionary preferred name. In the summary table, each patient is only counted once for each medication, on a preferred name level.

The safety set by treatment group will be used for this presentation.

6.3.10 Adverse Events

AEs and SAEs will be coded according to the Medical Dictionary for Regulatory Activities (MedDRA) system and tabulated by System Organ Class (SOC) and by preferred term for the 5-7-years follow-up visit.

The total number of patients with at least one AE and the total number of AEs will be presented by treatment group and in total. AEs with the same preferred term will be counted only once within a patient. The SAEs will be presented in the same way as the AEs.

The safety set will be used for these presentations.

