This protocol is written to describe the procedures for a single 5, 6 or 7 year follow-up control visit of patients that participated in the 12-month SCHEDULE-study and the following 3-year follow-up examination/visit. The aim of this 5 to 7-year follow-up visit is to examine the effect of long term treatment, i.e. 5, 6 or 7 years, with early initiation of everolimus (Certican®) and early elimination of cyclosporine (CsA), compared to standard immunosuppressive regimen including CsA, on renal and heart function. During the time period of this follow-up examinations this visit will be performed as part of a routine annual visit 5, 6 or 7 years since transplantation (and inclusion in the original SCHEDULE study).

PROTOCOL FOR THE 5 TO 7-YEAR FOLLOW-UP EXAMINATION

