4.3.7 Cardiac rejections

Number and grading of biopsy proven and treated rejections and rejections with hemodynamic compromise since the 3 year follow-up visit will be collected.

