4.5.2 Occurrence of Selected Adverse Events (Including Serious Adverse Events) – Main Categories

AEs considered clinically relevant are listed in Table 2. Any of these AEs that have occurred during the time between the 3-year follow-up visit and the 5 to 7-year follow-up visit should be registered in the case report form (CRF).

All SAEs should be reported to Novartis on specific SAE forms within 24 hours of learning of its occurrence to:

Clinical Safety Desk Fax:

To be answered: Has there been any occurrences of (clinically relevant) AEs since the 3-year follow-up visit i.e. from the 3-year follow-up visit to the 5 to 7-year follow-up visit.

The total number of each AE/SAE should be recorded, i.e. one patient may have experienced several AEs. Further details regarding collection and handling of AEs/SAEs are provided in Appendix 1.

• **Table 2 Selected Adverse Events – Main Categories**

Adverse Event	3 years to 5/7 years	
	AE	SAE
Infection		
Pneumonia		
Herpes Zoster		
Herpes simplex		
Sepsis		
Cancer		
Squamous cell carcinoma		
Basal cell carcinoma		
Other skin cancer		
PTLD		
Solid tumor		
Bone marrow toxicity		
Thrombocytopenia (<100000/ μ L)		
Leucopenia (<3500/ μ L)		
Anemia (<10 g/dL)		
Tromboembolic event		
DVT		
Pulmonary emboli		
Stroke/TIA		
Gastrointestinal system		
Diarrhea		
Constipation		
Pain		
Skin		
Rash		
Acne		
Hirsutism		
Cardiac		
Cellular rejection (grade)		
Humoral rejection		
LV dysfunction (EF<30%, or 25%↓)		
Arrhythmias (clinically significant, requiring treatment)		
PCI		
Myocardial infarction		

Adverse Event	3 years to 5/7 years	
	AE	SAE
Renal		
Proteinuria (albumin/creatinine >100)		
Hyperuricemia		
Peripheral oedema		
Gingival hyperplasia		
Other		

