The number of patients with at least one cardiac rejection (grade I-III): cellular, humoral or mixed, will be presented by treatment group for three periods: during the main study, between main study to 3-years follow-up and between 3-years follow-up to 5-7-years follow-up.

Also the total number of cardiac rejection (grade I-III): cellular, humoral or mixed, and the total number of treated cardiac rejection will be presented by treatment group for the three periods.

Information regarding mixed cardiac rejection was only collected for during the main study and 3-years follow-up. During main study and at the 3-years follow-up visit, date of when a biopsy performed was collected. A biopsy confirmed rejection within 13 days from previous biopsy confirmed rejection was considered the same event. Thus, the same rejection could go on for several weeks.

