14.3.9 Concomitant Medication at 5-7-years Follow-Up Visit

7.2 Graphs (Section 14.2-14.3 in ICH E3)

None

7.3 Listings of Individual Patient Data and other Information to be Produced for the Clinical Study Report (Sections 16.1 and 16.2 according to ICH E3)

(Listing numbers refer to Appendix number in ICH E3. CRF check questions/reminders will not be listed.)

- 16.1.7 Randomisation Scheme (*Copy of List, included in CSR for 12 Months*)
- 16.2.1.x Discontinued Patients, Reason for Discontinuation (from 3-years follow-up to 5-7 follow-up visit)
- 16.2.1.x Visit Dates and Other Important Dates
- 16.2.1.x *Study Termination – Not Applicable*
- 16.2.2 Protocol Deviations
- 16.2.3.x Patients Excluded from the Efficacy Analysis (Evaluable, Reason for Evaluable Classification)
- 16.2.3.x Treatment Allocation and Evaluable for All Patients
- 16.2.4.x Demographic Data
- 16.2.4.x Inclusion Criteria Not Met and Exclusion Criteria Met
- 16.2.5 Compliance and/or Drug Concentration Data
 - Immunosuppressive Medications
 - Immunosuppressive Level
- 16.2.6 Individual Efficacy Response Data
 - mGFR (mL/min/1.73m²)
 - IVUS (performed yes/no and date)
 - Echocardiography

- SF-36
- EQ-5D
- BDI form
- [REDACTED]

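### Adverse events and last-period rejections are tabulated as counts over a window of 2, 3 or 4 years per patient, with no time denominator, so a difference in visit timing between arms cannot be told apart from a difference in event rate

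*SAP*

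**What the plan says.** The protocol's opening paragraph describes "a single 5, 6 or 7 year follow-up control visit of patients that participated in the 12-month SCHEDULE-study". Section 4.5.2 sets the AE window: "Any of these AEs that have occurred during the time between the 3-year follow-up visit and the 5 to 7-year follow-up visit" are to be registered, and every occurrence is counted, since one patient may have several. Section 4.3.7 uses the same starting point for the rejection data: "rejections with hemodynamic compromise since the 3 year follow-up visit will be collected". The number of AEs and SAEs is a listed endpoint (protocol section 2, SAP 3.3).

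For analysis, SAP 6.3.10 states: "The total number of patients with at least one AE and the total number of AEs will be presented by treatment group". It then adds: "AEs with the same preferred term will be counted only once within a patient". SAEs are presented in the same way. SAP 6.3.11 and tables 14.3.8 give patients with at least one rejection, total rejections and treated rejections by arm for three periods: "during the main study, between main study to 3-years follow-up and between 3-years follow-up to 5-7-years follow-up".

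No readable part of the SAP plans patient-years, event rates, time-to-event methods, a breakdown by visit year or a summary of follow-up time by arm for these outcomes. The dose rate in SAP 6.3.8 concerns drug exposure only. The dates needed are available: SAP Appendix 1, section 7.3, plans a listing titled "Visit Dates and Other Important Dates".

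**The concern.** A patient seen at year 7 is nominally observed for twice as long as one seen at year 5. The expected number of events rises with the window, and so does the chance of having at least one. If one arm happened to have more year-7 visits, it would show more AEs, more SAEs and more last-period rejections at the same underlying rate. The planned tables would give the reader no means of noticing, because observation time is not shown beside the counts. What is at stake is how a stated safety endpoint is read, not the mGFR analysis.

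The three rejection periods raise a separate question. Their nominal lengths are about 1 year, about 2 years, and 2 to 4 years. The first two are about the same for every patient, so their unequal lengths affect comparison across periods, not between arms. Only the third varies from patient to patient.

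**Working it through.** The documents give no event rate, no distribution of visit years and no sample size (SAP 4.2 calls it not applicable), so there is no stated figure to reproduce. The rates, visit-year mixes and arm sizes below are assumptions.

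1. **Windows.** From the visit definitions: 5 − 3 = 2, 6 − 3 = 3 and 7 − 3 = 4 years. These are nominal; actual intervals depend on visit dates.

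2. **All-occurrence counts.** At a constant rate λ the expected count is λt, so a 4-year window gives 4/2 = 2 times the count of a 2-year window.

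3. **At least one event.** The probability is 1 − exp(−λt). At 2, 3 and 4 years:
   - λ = 0.1 per year: 18.1%, 25.9%, 33.0%
   - λ = 0.2 per year: 33.0%, 45.1%, 55.1%
   - λ = 0.5 per year: 63.2%, 77.7%, 86.5%

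   A count capped at one per preferred term per patient behaves like this within each term. From 2 to 4 years it grows by a factor of 33.0/18.1 = 1.82, 55.1/33.0 = 1.67 or 86.5/63.2 = 1.37, that is, less than two-fold, and less so the commoner the event.

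4. **Effect of unequal visit mix at equal true rates.** With visit years 5/6/7 at 50/30/20% in one arm and 20/30/50% in the other, the mean windows are 0.5×2 + 0.3×3 + 0.2×4 = 2.7 and 0.2×2 + 0.3×3 + 0.5×4 = 3.3 years. The ratio of all-occurrence counts is 3.3/2.7 = 1.22. A milder imbalance (40/30/30% v 30/30/40%) gives 3.1/2.9 = 1.07. The bound, all year 5 v all year 7, is 2.00. With identical mixes the ratio is 1.00. Dividing by patient-years returns 1.00 in every case.

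5. **What chance alone can do.** If visit years are equally likely, the window has SD √(2/3) = 0.816 years and mean 3 years. The 102 patients who attended the 3-year visit give at most 51 per arm if split evenly; 46 is taken as a lower value.
   - 46 per arm: SE of the difference in mean window = 0.816 × √(2/46) = 0.170; 1.96 × 0.170 = 0.33 years; 0.33/3 ≈ 11.1%.
   - 51 per arm: 0.816 × √(2/51) = 0.162; 1.96 × 0.162 = 0.32 years; 0.32/3 ≈ 10.6%.

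   A simulation of 100,000 runs with 51 per arm gave a 95% range of 0.90 to 1.11 for the ratio of mean windows, and 0.88 to 1.14 (rounded) with 35 per arm.

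6. **Across rejection periods.** A constant 0.2 per year would give 20, 40, and 40 to 80 rejections per 100 patients in the three periods. This shows only that the counts cannot be read as a trend. Step 7 shows why rates would not fully mend that.

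7. **Ascertainment in the last period.** SAP 6.3.11 says that mixed rejection was collected only for the main study and the 3-year follow-up. It also reports biopsy dates only for those two, and the rule that merges rejections confirmed within 13 days of each other needs those dates. The third period is therefore not measured in the same way.

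**The case against.** The strongest reply is that these tables are descriptive. The only stated hypothesis test is on mGFR. The endpoint is defined as a number of events, and the SAP reports a number of events. That stands: nothing here is a flawed test, and any rate ratio should be labelled descriptive.

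Second, counts mislead between arms only if the visit-year mix differs by arm. The visit is a routine annual one whose year depends largely on time since transplantation, and nothing in the documents ties it to treatment. That stands too. A reader might infer that the planned tables are biased against one arm; the documents show no mechanism for that. What remains is that the study is open-label, attendance decides who is seen and when, and no check of follow-up time by arm is planned.

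Third, ±11% is a 95% limit under an assumed even spread, and it is modest beside ordinary count noise. With an assumed 100 Poisson events per arm, the SE of the log ratio is √(2/100) = 0.141. Adding one SE of window imbalance (0.170/3 = 0.057) in quadrature gives 0.152, about 8% wider. That is fair as to size. But this component can be removed using dates already held.

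Fourth, the once-per-term rule means that the SAP's AE count does not grow in proportion to time, and a model with log patient-years as offset would not suit it. This is correct, so the numerator must be named before any rate is calculated.

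Fifth, a reader might infer from unequal periods that the rejection table would show a false rise over time. The periods are labelled, the true course of the rate is unknown, and ascertainment changes in the last period, so the documents do not support a claim about what the trend would show.

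Finally, the listed visit dates let a determined reader reconstruct follow-up by hand. That helps little where the summary tables are what is read.

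**Conclusion.** The point holds as a gap in presentation. AEs, SAEs and third-period rejections accumulate over a nominal 2, 3 or 4 years, and the planned tables contain nothing that separates visit timing from event rate. The actual distortion is unknown and may be nil. Chance alone could move the ratio of mean windows by about ±11% (95% range), assuming an even spread of visit years and 46 to 51 patients per arm. The figure applies in full to counts of all occurrences and only as an upper guide to the once-per-preferred-term count. It does not touch the primary analysis. The statement about missing time denominators rests on the readable text; some of the SAP is redacted.

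**What to change.** In SAP 6.3.10, 6.3.11 and tables 14.3.1 and 14.3.8, keep the planned counts and add the following.

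- **Follow-up time by arm:** a summary of the interval from the 3-year visit date to the 5-7-year visit date, with total patient-years.
- **Rates:** events per 100 patient-years with 95% CI by arm, and a descriptive rate ratio, for all recorded occurrences of AEs and SAEs (the count that protocol 4.5.2 records) and for treated rejections in the third period. State that the numerator is all occurrences, not the once-per-term count. The interval should allow for several events in one patient.
- **Patients with at least one event:** present by visit year, or use time to first event where event dates exist.
- **Three rejection periods:** show patient-years for each period, with a footnote that ascertainment differs in the last one, so rates across periods are not directly comparable.

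The cost is a little extra programming; visit dates are already collected. One limit remains: the safety set requires an assessment at the 5-7-year visit (SAP 5), so patients never assessed there contribute neither events nor time, and patient-years do not recover them.

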2 AIMS/OBJECTIVES

The major aim of this extension study is to evaluate the long-term (i.e. 5 to 7 years) effect of early initiation of everolimus and early elimination of CsA compared to standard immunosuppressive regimen including CsA on primary and secondary endpoints investigated in the SCHEDULE main study. The endpoints for this 5 to 7-year follow-up visit are:

Primary endpoint:

- Renal function as assessed by measured glomerular filtration rate (mGFR)

Secondary endpoints:

- Progression of CAV by IVUS analysis
- Myocardial structure and function by echocardiography assessment
- Quality of life by SF-36 (Minnesota Living with Heart Failure Questionnaire), Euro Quality of Life 5D (EQ 5D), and Beck Depression Inventory (BDI) form
- Number of adverse events (AEs)/serious adverse events (SAEs)

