4.5.3 Instructions for collecting and reporting Adverse Events and Serious Adverse Events

The purpose of this instruction is to guide how to collect and handle the side effects from a practical point of view.

- When the patient comes to the clinic visit, ask him/her if there have been any adverse events (clinically relevant) since the 3-year follow-up visit (i.e. between the 3-year follow-up visit and the 5 to 7-year follow-up visit).
- Record serious and non-serious AEs and the total number of each event in the CRF (each patient might have experienced several events).
- Check the adverse events/serious adverse events against medical records in order to source verify the events.
- The serious adverse events must be reported to Novartis within 24 hours of learning of its occurrence.
- State in the medical record for the study visit:
 - that the patient has been asked for clinically relevant adverse events
 - the events reported by the patient
 - refer to where in the medical record the different adverse events can be found (e.g. by date).
- If the reported adverse events cannot be verified in medical record/any other source document the patient should be asked if he/she has been in contact with a doctor/hospital and/or received treatment due to the event and attempt to retrieve this information from the treating physician/hospital. It is important to make an effort to find the medical records/source documents and to document this for the study visit in the medical records.
- As for the original study (CRAD001NO02, EudraCT number 2009-013074-41), everolimus (Certican®) is defined as the study drug. If the SAE is not previously documented in the IB or Package Insert for (new occurrence) and is thought to be related to the study drug a Drug Safety and Epidemiology Department associate may urgently require further information from the investigator for health authority reporting. Novartis may need to issue an Investigator Notification to inform all investigators involved in any study with the same study treatment that this SAE has been reported. Suspected Unexpected Serious Adverse Reactions will be collected and reported to the competent authorities and relevant ethics committees in accordance with EU Guidance 2011/C 172/01 or as per national regulatory requirements in participating countries.

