3.3 Safety Endpoints

Number of Adverse Events (AEs)/Serious Adverse Events (SAEs).

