6.1 Changes in the Planned Analyses

Minnesota Living with Heart Failure Questionnaire was not included in the study.

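### As written, SAP 6.3.10 counts repeat events under one preferred term only once per patient, so the promised total number of AEs (and SAEs) is not a count of events

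*SAP*

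**What the plan says.** SAP 6.3.10 opens by tabulating AEs and SAEs by system organ class (SOC) and preferred term. It then names two summary figures: "The total number of patients with at least one AE and the total number of AEs will be presented by treatment group and in total". The next sentence sets the counting rule: "AEs with the same preferred term will be counted only once within a patient". The one after extends the treatment to serious events: "The SAEs will be presented in the same way as the AEs".

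The number of AEs/SAEs is a secondary endpoint in protocol section 2 and the only safety endpoint in SAP 3.3.

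On data collection, protocol 4.5.2 says: "The total number of each AE/SAE should be recorded, i.e. one patient may have experienced several AEs". Protocol 4.5.3 instructs sites: "Record serious and non-serious AEs and the total number of each event in the CRF".

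**The concern.** The once-per-term rule directly follows the promise of a total number of AEs, and no words confine it to patient counts. A programmer who follows the text would remove repeat events of the same term within a patient before adding up. Events under different terms would all still count, but a second or third pneumonia in one patient would not.

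The endpoint is a number of events, and sites are told to record how many times each event happened. The summary would then discard what the protocol asked sites to collect. Collection covers the time from the 3-year visit to the 5-, 6- or 7-year visit, roughly two to four years. Table 2 of the protocol includes events that can recur in that time, such as pneumonia, basal cell carcinoma and diarrhea. Two programmers working from the same data could also report different totals for the same endpoint.

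**Working it through.** **Reading the text**

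1. The rule has no effect on the number of patients with at least one AE, since each such patient already counts once. Of the two figures named in that paragraph, it can change only the total number of AEs.
2. The subject of the rule is AEs, not patients. SAP 6.3.9, on concomitant medication, words its rule differently: there the patient is what is counted once, and the rule is tied to a named summary table.
3. Nothing elsewhere settles the matter. The AE entries in SAP Appendix 1 (14.3.1.x) are titles without a counting rule. SAP 6.1, on changes to the planned analyses, mentions only the Minnesota questionnaire.

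**A small hypothetical example**

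Patient 1 has three pneumonias and one herpes zoster. Patient 2 has one pneumonia.

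- All occurrences: 3 + 1 + 1 = 5 AEs.
- Rule as written: 2 terms for patient 1 plus 1 for patient 2 = 3 AEs.
- Patients with at least one AE: 2 either way.

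**Possible size**

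The plan has no figure to reproduce and gives no AE rates. Every rate below is an assumption.

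With mean m events per patient for a term, the rule keeps one event for each patient who has any. Over all terms:

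share lost = 1 − Σ P(at least one) / Σ m

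- Poisson: P = 1 − exp(−m).
- Negative binomial, variance m + k·m² with k = 1 (repeats clustered in patients): P = 1 − 1/(1 + m).

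For a single term under Poisson:

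- m = 0.05: 1 − (1 − exp(−0.05))/0.05 = 2.5% lost.
- m = 0.5: 1 − (1 − exp(−0.5))/0.5 = 21% lost.

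For the overall total, Table 2 of the protocol names 4 + 5 + 3 + 3 + 3 + 3 + 6 + 1 + 3 = 31 items, leaving out headings and the Other row. Removing cellular and humoral rejection, which have their own totals in SAP 6.3.11, leaves 29. Each item is treated as one preferred term, and M is the mean number of AEs per patient. Two spreads are used:

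- Even: m = M/29 for each item.
- Concentrated: half of all events in 3 items (m = M/6 each) and the rest over 26 items (m = M/52 each).

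| Share of total lost | M = 1 | M = 3 | M = 5 |
|---|---|---|---|
| Even, Poisson | 1.7% | 5.0% | 8.1% |
| Even, negative binomial | 3.3% | 9.4% | 14.7% |
| Concentrated, Poisson | 4.4% | 12.1% | 18.4% |
| Concentrated, negative binomial | 8.1% | 19.4% | 27.1% |

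One cell in full (concentrated, negative binomial, M = 3): kept = 3 × 0.5/1.5 + 26 × (3/52)/(1 + 3/52) = 1.000 + 1.418 = 2.418. Share lost = 1 − 2.418/3 = 19.4%.

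At M = 3, 100 patients have 300 recorded events. The table would show 285 (even, Poisson), 272 (even, negative binomial), 264 (concentrated, Poisson) or 242 (concentrated, negative binomial).

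**The case against.** The strongest reply is that the sentence was meant only for patient counts in the SOC and preferred-term table that opens SAP 6.3.10. A once-per-patient-per-term rule is natural there, and SAP 6.3.9 uses one for medication. The redundancy argument looks only at the two figures in the same paragraph and leaves that table aside. This reading is possible, and it may be what the authors intended. But the text does not state it, and the literal reading changes the total for a named endpoint.

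A second reply is that neither endpoint statement fixes a counting unit, and that recording every occurrence in the CRF is compatible with summarising by distinct term. That is so in principle, but a figure called the total number of AEs would then be something other than a number of events, without a label saying so.

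Third, the percentages rest wholly on assumed inputs. This stands. Items such as solid tumor, arrhythmias or pain may cover several preferred terms, and hyperuricemia or gingival hyperplasia may be persistent rather than recurrent. Both would lower the loss. Skin cancers and infections could repeat and raise it.

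Fourth, the consequence is limited. This also stands: no test on AEs is planned, AEs are listed by patient (16.2.7), serious events are listed in 14.3.2, and rejections have separate event totals.

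Last, counting all occurrences needs a definition of a new event, and SAP 6.3.11 describes one (13 days) only for biopsy-confirmed rejection. This is no obstacle here, because the CRF already holds the number of each event as recorded by the site.

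**Conclusion.** The concern holds. As written, SAP 6.3.10 makes the total number of AEs, and likewise of SAEs, a count of patient-by-preferred-term pairs. Wherever a patient has repeats under one term, that total understates the endpoint.

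The direction follows from the rule itself; the actual size cannot be determined from the documents. The modelled losses depend on the assumed event rates, their spread over Table 2 items, one preferred term per item, and k = 1 where clustering is allowed. The loss is small unless some terms recur often.

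The damage is confined to descriptive AE/SAE summaries and could be recovered by a recount from the listings. The number of patients with at least one AE and the primary mGFR analysis are unaffected, and the documents show no effect on the comparison of arms. It should be corrected because it concerns a named endpoint and costs almost nothing, but it does not threaten the trial's main conclusion.

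**What to change.** Amend SAP 6.3.10 to say that counting once within a patient applies only to the number and percentage of patients per SOC and preferred term, and that total AEs and total SAEs are computed from all occurrences recorded in the CRF.

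The cost is one sentence. The occurrence counts are already collected under protocol 4.5.2 and 4.5.3, and the total is already a planned figure, so no new data or table is needed.
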